The consent form will be translated into Spanish and submitted the IRB once it is ready. A copy of the English consent form is attached with this IRB package.

C6. Randomization

After a home visit to consent and collect baseline data, patients will be randomized in a 1:1 ratio, to receive either: (1) CAPABLE intervention or (2) usual care. The schedule will be stratified by surgical vs. non-surgical hospital admission due to the marked difference in functional recovery.¹³ Cases will be randomized within variable-sized blocks from 4 to 8 participants. These procedures will maintain allocation concealment throughout the trial, consistent with the CONSORT recommendations.¹⁴ No research staff or investigator interacting with potential participants will be able to anticipate treatment allocation of the next assignment because of variable block sizes.

C7. Patient interviews

Study participants will be asked to participate in one interview at the start of the study, a second interview 20 weeks later and a possible third interview in about 52 weeks post study enrollment. Each interview visit will last about 1 hour. During each visit, a trained research interviewer will ask the participant questions about their daily activities, pain level, medical conditions and other questions about their health (see Table 1 below). At the very end of the study, after all of the interviews are completed, another member of the research team may call and speak to the patient briefly about how the study went. All study participants will receive \$25 after each completed in-home interview.

Table 1. Data Sources

MEASURES (CITATION)	MEASURED WHEN	CONSTRUCTS AND MEASUREMENT ATTRIBUTES	TESTED IN SPANISH SPEAKING POPULATIONS
Demographics	BL, 20, 52 weeks	Age, race, sex, insurance attributes, live with others, reason for hospital stay,	Yes
ADLS – Katz ^{72,73,75} 0-16	BL, 20,52 weeks	Bathing, dressing (upper and lower), toileting, transferring, toileting, feeding, walking across small room. Cronbach's alpha 0.87-0.94. ⁷⁷	Yes
IADL 0-16 ⁷⁶	BL, 20,52 weeks	Ability to use the telephone, shop, prepare food, light housekeeping, wash laundry, take own medication, travel independently, and manage finances	Yes
Prior hx ADLs, IADLs	BL	ADL and IADL assessment prior to hospitalization	Yes
PROMIS Global 10	BL, 20,52 weeks	Overall health, quality of life, social activities, self-care, pain, fatigue, anxiety/depression, and mobility	Yes ⁷⁷

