Field interviewers trained in quality data collection will directly enter data into the Redcap data entry and management system. With patient permission, the interviews will also be audiotaped. Intervention staff will also record periodic visits with patient permission. The project manager will check data from screening, intervention sessions, and final data collection for completeness and appropriateness and will listen to recordings based on quality control protocols. There will be a Data Safety and Monitoring Board (DSMB) of senior researchers external to the project with expertise in research methods, and older adults to assure subject safety and adherence to human subject protection policies. Evaluation will include periodic assessments of data quality, participant recruitment, accrual, and retention.

Participants are part of a Medicare Advantage (MA) Managed care plan. Claims from the VNSNY CHOICE Medicare Advantage database will be used to identify study participants who were admitted to a hospital (planned and unplanned), skilled nursing facility, and/or nursing home at 90 days and during the 52-week follow-up period. Services will be identified from claims using facility and Current Procedural Terminology (CPT) codes. We will use data from VNSNY administrative records to identify participants who were readmitted to skilled home health care during the follow-up period.

E. Analytic Methods

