E1. Analytic Approach. The overall goal of this rigorous experimental study is to test the effectiveness of a multi-component homebased intervention to enhance physical function of patients who have ADL difficulties and been recently hospitalized. We will use intention-to-treat analysis (ITT) as the primary method to analyze the results; data from all participants will be analyzed as members of their assigned study group. We may analyze post randomization data (e.g., treatment compliance) in supplementary analyses, such as complier-average causal effect (CACE) models. In addition to the primary outcome, numerous comparisons will be conducted for the secondary outcomes. P-values from these secondary outcomes will be considered descriptive indicators of the intervention impact, and not as absolute indicators for null hypothesis testing, which might require p-value adjustments for inflated type I error rate due to multiple comparisons. For our primary analyses, we will use cases with complete data. We will also conduct sensitivity analyses comparing the complete case analysis with analyses that use multiple imputation for missing data. Models will compare imputation done 1) for all people with missing data, including deceased cases, and 2) for only those who survived but dropped out.

E2. Sample Size

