Sample size calculations are based on our ability to detect clinically meaningful effect sizes for CAPABLE on the primary outcome of mean ADL difficulty score. All calculations are based on two-sided tests of 0.05 significance. Assuming a conservative attrition rate of 25% during the 20-week follow-up period, (we have consistently had 13% attrition in prior CAPABLE studies)¹⁰ we would need to enroll 60, 85, and 134 participants per treatment arm to detect, with 80% power, an intervention effect size of 0.60, 0.50, and 0.40, standard deviation units, respectively, at 20 weeks after baseline. Preliminary data showed a 41% reduction in ADL difficulty (*0.76 standard deviation units*) in the post-hospitalized group.¹⁰ Smaller effects of 0.57 to 0.60 standard deviation units were noted for other outcomes, and effect sizes of 0.63 for ADL difficulties and 0.62 for IADL difficulties were obtained in a small RCT pilot.¹⁵ By enrolling at least 268 participants, we anticipate having 20-week outcome data (primary endpoint) on 200 participants after 25% attrition. This sample size will provide excellent power to detect clinically meaningful differences between intervention and usual care groups.

E3. Primary study aims:

- 1. Test the effectiveness of CAPABLE in reducing ADL difficulties compared to usual care after 20 weeks of intervention.** We will address this aim using an analysis of covariance on the 20-week Katz summary disability score with treatment group as the primary independent variable and the baseline Katz score as the primary covariate. Other baseline demographic (e.g., gender) functional ability, and clinical variables (e.g., Charlson comorbidity index, pre-hospitalization ADL function) will be included as covariates if there are any random imbalances on those variables across intervention groups or if they are significantly correlated with the 20-week Katz score after adjustment for the baseline Katz score.

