- 2. Estimate the impact of CAPABLE on subsequent health care utilization and costs, including all cause admission to hospital, skilled nursing facility, inpatient rehabilitation, skilled home health care at 52 weeks compared to intervention costs;** We will use time to event (i.e., survival analysis) models to examine intervention impact on discrete outcomes. We will use proportional hazards models with intervention group as primary predictor variable, adjusting for covariates. We will use hazard ratios and 95% confidence intervals to interpret whether the intervention was successful in reducing the rates (or delaying) these discrete event outcomes. The overall intervention cost model is: [1] $CTreat_i = \text{ingredient}_k \times \text{price}_k$ Where $CTreat_i$ is the total cost of intervention services delivered to the "i-th" participant and ingredient_k is the sum of the 'k-th" type of ingredient supplied to the "i-th" participant and price_k is the price of the k-th type of ingredient. Ingredients for each participant will be measured by building cost tracking modules into the individual contact tracking forms. The price of each home modification will be on a work order. *Medical Costs* will be estimated using claims data from control and treatment cohorts. The consent process will include permission to view patients' annual electronic Medicare claims summaries for all claim types including inpatient, outpatient, home health, physician outpatient, and durable medical equipment. The medical cost model will be based on the following model: [2] $CM_i = Service_{ik}$ where CM_i is the annual medical cost of participant "i" and $Service_{ik}$ is the Medicare/Medicaid allowable charge for the k-th service delivered to participant "i". The hypothesis that CAPABLE is cost-saving is a test that the $(cost\ of\ treatment - costs\ of\ medical\ utilization) \leq 0$. The first term can be estimated as $E(CTreatment_i)$ and the second term as $E(CM_i | Control) - E(CM_i | Treated)$. We propose to use a semi-parametric bootstrap estimator in which we will iteratively draw samples of $[E(CTreatment_i)] - [E(CM_i | Control) - E(CM_i | Treated)]$ and compute the proportion of the values below 0.

E4. Secondary study aims:

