The overall goal of this rigorous experimental study is to test the effectiveness of a multi-component home-based intervention to enhance physical function of patients who have ADL difficulties and have been recently hospitalized compared to a usual care control group. We will use an intention-to-treat (ITT) analysis to compare these two conditions; data from all participants will be analyzed as members of their randomly assigned treatment group. The primary outcome will be the Katz measure of difficulties with activities of daily living (ADLs). Scores on this measure range from 0 to 16, with higher scores indicating greater disability. In addition to the primary outcome, several additional comparisons will be conducted on secondary outcome variables. Because there is only one primary outcome measure, no adjustment for type I error is made for multiple comparisons, and a statistically significant finding will be indicated if the p-value is less than 0.05 for the treatment effect. This would indicate a type I error rate of less than 5% for rejecting the null hypothesis of no difference between treatment groups if the null hypothesis is, in fact, true. Two-tailed tests will be used for all statistical comparisons. P-values will also be reported for the secondary outcome analyses but these p-values from the secondary analyses will be considered descriptive indicators of the intervention impact on those measures and not as absolute indicators for null hypothesis testing.

Comparison Group Selection

This is a two group comparison. A total of 268 participants will be enrolled and randomized in a 1 to 1 ratio to either the intervention condition or to a usual care control group, with 200 participants expected to provide outcome data after accounting for 25% attrition. A total of 200 participants for analysis will provide 80% power to detect a clinically meaningful difference of 0.40 standard deviation units between intervention and usual care groups on the primary outcome measure of ADL difficulty.

Type of Statistical Test

This two group comparison will be a test of **superiority**. A two-tailed test will be used with the type I error rate set at 0.05.

Statistical Test of Hypothesis (Primary Outcome)

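### The 52-week cost comparison uses plain arm means of claims totals, with no valid rule for claims cut short when a participant leaves the health plan; the bias can run in either direction.

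*Combined protocol and SAP*

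**What the plan says.** The economic question is the second of two primary aims (section A), with a 52-week horizon. Section E3, item 2 builds each participant's medical cost from claims as a total that "is the annual medical cost of participant" i. The saving is the control-arm expectation minus the treated-arm expectation. A semi-parametric bootstrap of programme cost minus saving then gives the share of draws below zero. Item 2 contains no observation window, no rule for a partial year and no rule for death.

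On the data source, D2 states that "Participants are part of a Medicare Advantage (MA) Managed care plan" and draws admissions from that plan's claims database. C3.4 bases the ability to track usual-care cost on shared plan membership. E3, item 2 adds that consent will cover annual Medicare claims summaries, without saying whether these continue after a person leaves the plan. C4.1 requires membership as an entry criterion and does not require it to last to week 52.

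The general rule is in E1: analysis by assigned group, then "For our primary analyses, we will use cases with complete data", then multiple-imputation sensitivity analyses, one version covering the deceased and one restricted to surviving dropouts. The Statistical Analysis Overview covers the Katz score and time-to-event outcomes but contains no cost analysis.

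**The concern.** Two kinds of early ending need different treatment. After plan exit, care continues but its claims may no longer be seen, so the cost is missing. After death the cost is truly zero, so the total is known if the person was enrolled until death. A plain mean of totals treats both alike. The Cox models in the same item can censor a person who leaves; an arm mean of 52-week totals cannot.

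Programme cost comes from the study's own contact forms and work orders, so plan exit does not reduce it. Lost claims therefore affect only one side of the comparison that decides whether the programme pays for itself.

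**Working it through.** **Inputs from the documents.** 52-week horizon (section A); difference of arm means (E3, item 2); 134 per arm (E2), where "patients will be randomized in a 1:1 ratio" (C6); handyman budget of at most $1,500 per household (C3.3).

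**Inputs not in the documents, assumed here.** Mean annual cost $20,000, even spending over the year, exits uniform over the year (half a year lost on average), and exit rates of 8% to 20%. The 25% attrition in E2 ("Assuming a conservative attrition rate of 25% during the 20-week follow-up period") concerns the 20-week interview and is not a plan-exit rate.

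**Plan's own figure.** The only sizing is for the ADL score: "we would need to enroll 60, 85, and 134 participants per treatment arm to detect, with 80% power" effects of 0.60, 0.50 and 0.40 SD. A two-sided t-test at 0.40 SD needs 99.08, rounded up to 100; 100 / 0.75 = 133.3, so 134. This matches, but it says nothing about cost. It serves below only as the arm size.

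**Step 1: claims after exit counted as zero.** Let C be the control mean, S the true saving, and qC and qT the exit proportions in control and CAPABLE.

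Observed saving = C(1 − qC/2) − (C − S)(1 − qT/2)

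Bias = C(qT − qC)/2 − S·qT/2

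- S = 0, qT − qC = +0.04: 20,000 × 0.04 / 2 = $400 false saving. Reversed, it is a $400 false loss.
- S = 0, qC/qT = 10%/20%: $1,000 false saving. At 20%/10%: $1,000 false loss.
- S = $3,000, both 10%: bias = −3,000 × 0.05 = −$150, so $2,850 is seen (5% lost). Any programme cost between $2,850 and $3,000 would then wrongly appear not to be recovered.
- S = $3,000, 10%/20%: +1,000 − 300 = +$700, so $3,700 is seen. At 20%/10%: −1,000 − 150 = −$1,150, so $1,850 is seen.

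**Step 2: complete cases only.** Let completers average b and leavers r × b, the same in both arms. Bias = b(r − 1)(qT − qC).

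- b = $20,000, r = 2 to 3, 10%/20%: 20,000 × 1 × 0.10 = $2,000 to 20,000 × 2 × 0.10 = $4,000 overstatement. At 20%/10%: the same amount understated.
- r = 1: no bias. The result depends on leavers costing more than stayers, which the documents do not state.

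**Step 3: deaths, if E1 is read as excluding them.** Assume deaths of 12% in control and 8% in CAPABLE, decedents at $60,000 and survivors at $25,000 in both arms.

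- Control: 0.12 × 60,000 + 0.88 × 25,000 = $29,200
- CAPABLE: 0.08 × 60,000 + 0.92 × 25,000 = $27,800
- True saving $1,400; survivors only, 25,000 − 25,000 = $0

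The zero is built in by assuming equal survivor costs. Summing claims to death with nothing afterwards gives the right $1,400.

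**Step 4: size against noise.** If the cost SD equals the mean (assumed), the standard error of the difference is 20,000 × √(2/134) = 20,000 × 0.122, about $2,440. A $400 shift is 400/2,440 = 0.16 standard errors.

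A simulation used gamma costs (shape 0.7), 134 per arm, claims zero after exit, and programme cost and true saving both $3,000, so true net saving is zero. It gave the chance that the bootstrap share reaches 0.95, a threshold chosen here because the plan sets none:

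| Exit, control/CAPABLE | Chance |
|---|---|
| none | 5.6% |
| 15%/15% | 4.6% |
| 10%/20% | 8.8% |
| 20%/10% | 1.7% |

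With 1,000 simulated trials per row, the Monte Carlo error near 5% is √(0.05 × 0.95/1,000) = 0.7 points. The first two rows are not clearly different; the two imbalanced rows are.

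**The case against.** **E1 already deals with incomplete data.** A reader might infer that the plan makes no allowance at all. That goes too far: E1 commits to analysis by assigned group and to imputation sensitivity analyses. What stands is that E1 does not say whether it covers cost, and the Statistical Analysis Overview names only one primary outcome measure, the Katz score. No cost imputation model is given. Imputing survivors who left could be reasonable, but it is offered only as a sensitivity analysis.

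**Direction.** A reader might infer that lost claims always count as savings. They do not. A false saving needs more exit in the CAPABLE arm, and the documents give no reason to expect that. Equal exit cannot reverse the sign of the saving itself.

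**Deaths.** A reader might infer that the plan drops its costliest people. The documents do not say that leavers or decedents cost most. Because a decedent's claims may be fully known, they can fairly be called complete data, and a plain sum then handles death correctly. The death problem exists only if E1 is read as covering cost and excluding decedents.

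**Data source.** The Medicare claims summaries might cover people after plan exit. If so, much of the problem disappears, but the plan does not say so.

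**Eligibility and size.** C4.1 excludes people planning to relocate within a year and those with an OASIS rating for conditions that could cause death within a year. This lowers exit and death without ruling out a change of plan or an unexpected death. The small-imbalance bias is also modest beside sampling error. That argues for proportion in the claim; a bias of unknown sign remains in a primary-aim estimate.

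**Conclusion.** The concern holds for plan exit: neither the stated estimator nor E1 gives a valid 52-week mean cost when claims stop early. For death it holds conditionally, on one reading of E1. The sign of the bias cannot be predicted from the documents. Under the assumptions above, a 4-point exit imbalance shifts the saving by about $400 in either direction, and equal 10% exit removes about 5% of a true saving. Every dollar figure rests on assumed costs and exit rates and serves only to show scale. For comparison, the handyman component alone is capped at $1,500 per household, so shifts of this size matter when programme cost and saving are close. This should be changed before the cost analysis is run; it does not affect the ADL primary analysis.

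**What to change.** In E3, item 2, and in a matching cost section of the Statistical Analysis Overview:

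1. Take each participant's observation window from plan enrolment dates.
2. Keep all randomised participants in the cost analysis.
3. Count deaths as complete observations: actual cost to death, zero afterwards.
4. Establish whether the consented Medicare claims summaries cover people after plan exit. Unless that is confirmed, treat exit as censoring and estimate each arm's mean 52-week cost with a partitioned or inverse-probability-of-censoring-weighted estimator, recomputed within each bootstrap draw. State the assumption that exit is unrelated to later cost given the variables used.
5. Report plan exit and death by arm.
6. State that E1's complete-case rule and its imputation of deceased cases do not apply to claims costs.

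The cost is SAP text, retrieval of enrolment dates, modest programming and slightly wider intervals. No extra participants or visits are needed.

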- 1) Test the effectiveness of CAPABLE for reducing ADL difficulties compared to usual care baseline to 52 weeks.** Additional, multilevel longitudinal analyses will incorporate the 52-week outcome data to examine the maintenance of any intervention effects. In these models, time since randomization (20 vs. 52 weeks) will be examined as a within-person or repeated measures factor, and group*time interaction tests will determine whether there are different trajectories of change in ADL (primary outcome) and the other continuous secondary outcomes (IADL, depressive symptoms).
- 2) Explore whether the intervention has differential effectiveness across subgroups.** We will explore subgroup effects and heterogeneity of intervention response. Key subgroups will include those defined by gender, ethnicity, living arrangement, (e.g., with vs. without a co-residing caregiver), type of hospitalization (e.g., surgical vs. nonsurgical) and medical complexity (e.g., high vs. low Charlson comorbidity scores). We will add interaction terms to the models to test empirically whether the intervention is more or less effective in one group compared to a reference group, and examine stratified analyses where we observe significant interaction effects.
- 3) Examine theoretically-driven mediation pathways to identify potential mechanisms of intervention effectiveness.** We hypothesize multiple intermediate variables as possible mediators of the intervention's impact including changes in depression, pain, and control strategy use. For each of these

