The **method** to be used to calculate the p-value given the null hypothesis of no difference between the two treatment groups is an analysis of covariance (ANCOVA). The outcome variable will be the 20-week Katz summary disability score. Treatment group (intervention vs. usual care control) will be the primary independent variable. The baseline (pre-treatment) Katz summary disability score will be the primary covariate. Other baseline demographic (e.g., gender), functional ability, and clinical variables (e.g., Charlson comorbidity index, pre-hospitalization ADL function) may be included as additional covariates if there are any random imbalances on those variables across intervention groups or if they are significantly correlated with the 20-week Katz score after adjustment for the baseline Katz score.

Method of Estimation (Primary Outcome)

An ordinary least squares estimate of the mean difference, adjusted for covariates, will be used. Consistent with the pre-specified type I error rate of 0.05, 95% confidence intervals will be reported for this covariate-adjusted mean difference.

Parameter Dispersion Type (Primary Outcome)

The standard error of the mean will be used to characterize dispersion and to calculate the 95% confidence interval.

Statistical Tests of Hypotheses (Secondary Outcomes)

Secondary outcomes include discrete events such as hospitalization and admission to skilled home health care, skilled nursing facility, and nursing home. Time to event (i.e., survival analysis) models will be used to examine intervention impact on these discrete outcomes. Cox regression (proportional hazards) models will be conducted with intervention group as the primary predictor variable and baseline demographic (e.g., gender), functional ability, and clinical variables (e.g., Charlson comorbidity index, pre-hospitalization ADL function) included as covariates.

Method of Estimation (Secondary Outcomes)

Hazard ratios (with usual care as the reference group) will determine the degree to which the intervention was effective in reducing the rates of (or delaying) these discrete event outcomes. All hazard ratios will be accompanied with 95% confidence intervals to aid interpretation and to characterize potential variability of the true intervention effect.

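### The longitudinal models for the 52-week aim do not say that the baseline outcome is included and name no 52-week group contrast; the only named test cannot answer the aim

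*Combined protocol and SAP*

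**What the plan says.** Protocol section E4, aim 1, sets the aim as "Test the effectiveness of CAPABLE for reducing ADL difficulties compared to usual care baseline to 52 weeks". Section A words it as testing the effect on ADL function at 52 weeks.

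The method in E4 is: "Additional, multilevel longitudinal analyses will incorporate the 52-week outcome data to examine the maintenance of any intervention effects". On the time factor it says: "In these models, time since randomization (20 vs. 52 weeks) will be examined as a within-person or repeated measures factor". The only test it specifies, of group by time, is meant to detect "different trajectories of change in ADL (primary outcome) and the other continuous secondary outcomes (IADL, depressive symptoms". No covariate is listed and no visit-specific group difference is named.

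Elsewhere the plan is explicit about baseline. Protocol section E3 specifies the primary 20-week ANCOVA "with treatment group as the primary independent variable and the baseline Katz score as the primary covariate", and the SAP repeats this under Statistical Test of Hypothesis (Primary Outcome): "The baseline (pre-treatment) Katz summary disability score will be the primary covariate". The mediation models in E4, aim 3, use baseline-adjusted changes.

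The SAP does not fill the gap. Its section on tests for secondary outcomes reads: "Secondary outcomes include discrete events such as hospitalization and admission to skilled home health care, skilled nursing facility, and nursing home". It then gives Cox models only, with no model for IADL, depressive symptoms or the 52-week ADL score. Table 1 of the protocol schedules the Katz ADL, IADL and PHQ-9 measures at baseline, 20 and 52 weeks, so the baseline values will be available.

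**The concern.** There are two linked gaps.

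First, the named test does not match the aim. A benefit that is fully kept from 20 to 52 weeks and no benefit at either visit both give a zero group by time interaction. A non-significant result would be read as maintenance in one case and would mean nothing in the other. Only the group difference at 52 weeks separates the two, and the plan does not name it as the estimate.

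Second, that 52-week difference is where a baseline covariate earns its keep. An analyst who fits exactly the terms listed (group, time, group by time) would compare follow-up scores without using baseline. The intervals would be wider than those an ANCOVA-type model gives, and more exposed to chance baseline imbalance.

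**Working it through.** **Inputs from the documents.** Two-sided alpha 0.05, 80% power, effects of 0.60, 0.50 and 0.40 SD, 25% attrition by 20 weeks, 60, 85 and 134 enrolled per arm, 200 analysed at 20 weeks (protocol E2; the SAP repeats the 268, the 200 and the 0.40 SD). Allocation 1:1 (protocol C6).

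**Inputs assumed.** The documents give no correlation r between baseline and follow-up scores, so a range is used. They give no expected number at 52 weeks, and two places call the 52-week interview only possible (the opening summary and C7). I take 90 per arm, and show 100 per arm as well.

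**1. The plan's own figure.** For 0.40 SD, n per arm = 2 × (1.96 + 0.8416)² / 0.40² = 98.1, so 99; 99 / 0.75 = 132. With the t-test, 100 per arm; 100 / 0.75 = 133.3, so 134 as stated. The same methods give 59 (normal) or 60 (t-test) for 0.60 SD, and 84 or 85.3 for 0.50 SD, against 60 and 85 stated. Power with 100 per arm at 0.40 SD is 80.7% (normal) or 80.4% (t-test), against 80% stated. These figures reproduce with no baseline covariate, so they are the right reference for the unadjusted contrast.

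**2. Group difference at one visit.** With outcome SD 1 and n per arm:

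- without baseline, SE = √(2/n)
- with baseline as covariate, SE = √(1 − r²) × √(2/n)
- variance ratio, without to with = 1 / (1 − r²)
- power ≈ Φ(effect / SE − 1.96)

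For n = 90, √(2/90) = 0.149. Without baseline at 0.40 SD: 0.40 / 0.149 − 1.96 = 0.72, power 77%. With r = 0.5: SE = 0.866 × 0.149 = 0.129; 0.40 / 0.129 − 1.96 = 1.14, power 87%.

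| Model (90 per arm) | Variance ratio | SE | Power, 0.40 SD | Power, 0.30 SD |
|---|---|---|---|---|
| No baseline | – | 0.149 | 77% | 52% |
| Baseline, r = 0.4 | 1.19 | 0.137 | 83% | 59% |
| Baseline, r = 0.5 | 1.33 | 0.129 | 87% | 64% |
| Baseline, r = 0.6 | 1.56 | 0.119 | 92% | 71% |

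With 100 per arm at 0.40 SD, power is 81% without baseline, and 84%, 87%, 90%, 94%, 98% and above 99% for r = 0.3, 0.4, 0.5, 0.6, 0.7 and 0.8. The variance ratio runs from 1.10 to 2.78 over that range.

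**3. The group by time term.** Let r1 and r2 be the correlations of baseline with the 20- and 52-week scores, and r12 that between the two follow-up scores. The variance factor of the 52-minus-20 contrast is 2(1 − r12) without baseline and 2(1 − r12) − (r2 − r1)² with it.

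- r1 = r2: no change.
- r1 = 0.6, r2 = 0.5, r12 = 0.7: 0.60 against 0.59; SE ratio √(0.59/0.60) = 0.99.
- r1 = 0.7, r2 = 0.5, r12 = 0.7: 0.60 against 0.56; SE ratio 0.97.

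So the named test gains at most about 3% in SE in these cases.

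**4. Bias.** A simulation of 4,000 trials (100 per arm, complete data, r1 = 0.6, r2 = 0.5, r12 = 0.7, true differences −0.40 and −0.30) gave mean estimates of −0.40 and −0.30 with and without baseline. The SEs without and with baseline were 0.142 and 0.115 at 20 weeks, and 0.139 and 0.122 at 52 weeks. Only precision differs.

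**5. What the interaction can show.** With differences of −0.40 at both visits, the interaction is −0.40 − (−0.40) = 0. With no difference at either visit it is 0 − 0 = 0. The test cannot tell these apart.

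**The case against.** The strongest reply is that the section is silent and excludes nothing. It lists no covariates at all. It describes these analyses as additional to a baseline-adjusted ANCOVA, and it speaks of change from baseline. A time factor with levels 20 and 52 weeks is also the usual layout when baseline is a covariate, so the quoted sentence is compatible with the fix. This stands: a reader might infer that the authors chose to leave baseline out, and the text does not support that. It also does not say that baseline is in, although the plan says so elsewhere when it means it.

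The power figures concern a visit-specific difference, whereas the test named is group by time, which hardly gains. That is correct, but the named test does not deliver the aim; the 52-week difference does.

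A reader might also infer that contrasts without baseline are biased, or that a 20-week ADL estimate from such a model would contradict the primary result. Neither follows. Under randomisation with complete data, the follow-up difference and the difference in change have the same expectation. Two 20-week estimates would differ by sampling variation around one target, and might still differ after the fix because the ANCOVA may carry further covariates.

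Finally, p-values for secondary outcomes are declared descriptive (protocol E1 and SAP overview). This lowers the weight of the power figures. It does not lower the value of narrower confidence intervals, on which descriptive reporting rests.

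**Conclusion.** The point holds as a gap in specification with a practical cost. E4, aim 1, does not state that the baseline outcome enters the longitudinal models and names no 52-week group contrast. Its one named test addresses only change between 20 and 52 weeks, so it cannot alone answer an aim that runs from baseline to 52 weeks.

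The cost in precision is conditional on baseline actually being omitted, and it falls on the visit-specific differences. It rests on the assumed correlations and on the assumed 90 per arm: over r = 0.4 to 0.6 the loss at 0.40 SD is about 6 to 15 percentage points of power. The direction does not depend on those assumptions: any nonzero correlation favours adjustment, apart from a negligible loss of degrees of freedom. The point covers the outcomes the section names (ADL, IADL, depressive symptoms) and leaves the primary 20-week ANCOVA and its conclusion unaffected.

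**What to change.** In protocol section E4, aim 1, and in a matching SAP entry for continuous secondary outcomes, state that:

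- each longitudinal model includes the baseline value of the same outcome as a covariate, with a baseline by time term (or, equivalently, treats baseline as an occasion with the group means constrained equal);
- the adjusted group differences at 20 and 52 weeks are reported with 95% confidence intervals;
- the 52-week difference is the estimate for this aim, with group by time kept as the test of whether the effect changes between the two visits.

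The cost is a few sentences of text. Table 1 already schedules all the baseline measurements, so no data, visits or participants are added.
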